SAE	serious adverse event
SAP	statistical analysis plan
SAS	Statistical Analysis System
SD	standard deviation
SE	standard error
SGLT2	sodium glucose cotransporter-2 inhibitor
SUSAR	suspected unexpected serious adverse reaction
T2DM	type 2 diabetes mellitus
TEAE	treatment-emergent adverse event
UGT	UDP-Glucuronosyltransferase
US	United States

Amendment Page – Summary of Changes (December 30, 2020)

Section #	Original Text/Figure	Amended Text/Figure	Rationale
1.2	Figure 1	Figure 1	Changed entry criterion for KCCQ <80 incorporated
1.4	Added text	After approximately 10 months, the planned enrollment in this study is not expected to reach the target of 1900 participants by the end of January 30, 2021 (the scheduled end of study enrollment window). Instead, the final anticipated enrollment may be in the range of about 400-480 participants. Consequently, a reduction in total sample size of this magnitude will have impact on statistical power at different effect sizes, as shown by the figure below. A large effect size was reported in the recently concluded DEFINE-HF study ¹⁷ . Additional KCCQ domains were also reported in this study with robust improvements over baseline ^{17,18} .	Statement about lower than expected sample size enrollment and its impact on statistical power
2.3.2.	Added full analysis set (FAS) definition	This includes all randomized participants who have received at least one dose of study intervention/medication and have at least one post-baseline KCCQ measurement. Analyses of the primary, secondary, and exploratory endpoints will be based on the full analysis set (FAS).	Primary, secondary, and exploratory endpoints will be based on FAS (earlier version stated as based on all randomized set)
5.2.2.	Population: all randomized set	Population: FAS - all randomized participants with HF (who either have HF _r EF or HF _p EF, regardless of T2DM status) with at least one dose of study intervention and at least 1 post-baseline KCCQ measurement	Changed analysis population to FAS
5.2.3.	Added to the analysis method	Mortality in this short-duration trial is expected to be low and to be comparable between groups and will be ignored in the primary analyses of mean differences in changes in KCCQ Total Symptom scores, but can be included in the responder analyses by assigning them to the lowest response (greatest deterioration) category. Should there be a >5% mortality rate and if it is unequally distributed between treatment arms, then joint modeling of survival and health status will be performed. A win-ratio approach ^{19,20} may also be considered by analyzing the KCCQ-TSS score as a composite, rank-based outcome, incorporating participant vital status at 12	Added to the analysis method regarding missing data due to deaths

		weeks along with a change in score from baseline to 12 weeks in surviving participants. This essentially is the rank analysis of covariance method, with a corresponding win ratio used to estimate the magnitude of treatment effect.	
5.3.2.	Population: all randomized set	Population: FAS - all randomized participants with HF (who either have HFrEF or HFpEF, regardless of T2DM status) with at least one dose of study intervention and at least 1 post-baseline KCCQ measurement	Changed analysis population to FAS
5.3.3.	Added to analysis method	The first key secondary endpoint will be analyzed following the same approach as employed for the primary effectiveness endpoint (i.e. using an MMRM model).	Added to analysis method regarding daily step counts from two-sample t-test to MMRM analysis
References	Added references	
Nassif, M. et al. (2019). Dapagliflozin Effects on Biomarkers, Symptoms, and Functional Status in Patients With Heart Failure With Reduced Ejection Fraction - The DEFINE-HF Trial. Circulation, Vol. 140, No. 18, 1463-1476
 
Bhatt, D. et al. (2020). Sotagliflozin in Patients with Diabetes and Recent Worsening Heart Failure. N Engl J Med, 2020; Nov 16
 
Gasparian, S. et al. (2019). Adjusted Win Ratio with Stratification: Calculation Methods and Interpretation, Stat.ME
 
Wang, D. and Pocock, S. (2016). A win-ratio approach to comparing continuous non-normal outcomes in clinical trials, Pharmaceutical Statistics, online 11 March 2016
	Added more references pertaining to sample size section and analysis methods such as win-ratio

1. INTRODUCTION

This Statistical Analysis Plan (SAP) describes the planned analysis and reporting for the 28431754HFA3002 (**Canagliflozin: Impact on Health Status, Quality of Life, and Functional Status in Heart Failure – CHIEF-HF**) study. This Phase 3b study is being conducted in the United States (US) in participants with symptomatic HF stratified by HF (reduced ejection fraction [HFrEF] or preserved ejection fraction [HFpEF]) and compares the effectiveness of canagliflozin 100 mg versus placebo for improvement in HF symptoms measured by the Kansas City Cardiomyopathy Questionnaire - Total Symptom Score (KCCQ-TSS) (see [Appendix 1: The Kansas City Cardiomyopathy Questionnaire \(KCCQ\)](#)) after 12 weeks. This document contains details of the relevant definitions, data handling conventions and methods for analyses. The document will be finalized prior to database lock.

This SAP is based on the clinical study protocol (finalized first on 7 November, and subsequently amended on 7 February 2020 (Protocol **28431754HFA3002 Amendment 1**, dated **07 February 2020 - EDMS-ERI-154820237, version 3.0**) by Janssen Scientific Affairs, LLC) that provides details on the conduct of this study and operational aspects of clinical assessments and timing for completing a participant in this study.

Based on the last protocol amendment, changes were made to this SAP on December 30, 2020 and are listed on the preceding amendment page in this document. A final version of this SAP with editorial changes is posted on 1 July 2021.

1.1. Objectives

Primary Objective

The primary objective is to determine the superiority of the effectiveness of canagliflozin 100 mg daily versus placebo in participants with symptomatic HF in improving the overall KCCQ-TSS.

Secondary Objectives

The first key secondary objective is:

- to determine the superiority of the effectiveness of canagliflozin 100 mg daily versus placebo in improving the total daily step count.

The second key secondary objective is:

- to determine the superiority of the effectiveness of canagliflozin 100 mg daily versus placebo in improving the KCCQ individual domain scores (physical limitation, quality of life, clinical summary, and overall).

Exploratory Objectives

The exploratory objectives are to assess the effectiveness of canagliflozin 100 mg daily versus placebo in participants with symptomatic HF by:

- responses on the Patient Global Impression of Change (PGIC) and the Patient Global Impression of Severity (PGI-S)
- healthcare resource utilization (HRU) and health economics data
- associations (correlations and/or categorical association measures) between digital markers (step count and floors climbed), and clinical events such as need for outpatient intravenous therapies, emergency department (ED) visits, and hospitalizations
- daily floors climbed
- time to first hospitalization/readmission for HF
- time to first hospitalization/readmission for other events
- time to death
- the participant's satisfaction with their experience with the virtual design at the end of the study (see [Appendix 2: Participant Satisfaction Survey](#)).

1.2. Study Design

OVERALL DESIGN

This is a randomized, double-blind, placebo-controlled, decentralized, virtual, superiority study conducted in the US in participants with symptomatic HF (stratified by heart failure with HFrEF or HFpEF). This study examines the improvement in the KCCQ-TSS after 12 weeks of treatment with canagliflozin 100 mg or placebo. The study will continue for an additional 6 months without further study intervention to collect participant follow-up data from the smartphone, Fitbit, and claims in a real-world setting. At the end of the 12-week, double-blind treatment period, participants will be informed about their actual treatment allocation, whether they had been randomized to canagliflozin or placebo.

The study will enroll participants from large integrated health networks (IHNs) and physician practices in the US with the participants conducting many of their study-related activities through an app on a smartphone and will provide daily activity data recorded by using a Fitbit device. There will be no in-person clinic visits required by the study (see [Appendix 3: Schedule of Activities](#)).

[figure not shown]
The study consists of a screening period, a 12-week double-blind treatment period, and a 6-month follow-up (no intervention) observational period for each participant. Approximately 1,900 participants are planned for randomization into the study in a 1:1 ratio to canagliflozin 100 mg daily or placebo groups (950 in each study intervention group). After Week 12 (i.e., the end of the double-blind treatment period), the study will continue for an additional 6 months when study intervention will no longer be provided. Randomization will be performed using the interactive web response system (IxR). Participants will be stratified based on HF ejection fraction (EF) type – HFrEF or HFpEF.

Data collection from the smartphone, Fitbit device, and claims will continue until Month 9 for all endpoints. Specifically, study assessments include the following: KCCQ, PGIC, PGI-S, and an

optional participant satisfaction survey at end of study (via smartphone), step count and floors climbed (via the Fitbit device), medical and pharmacy claims data (including up to 36 months history for eligibility confirmation), HRU and health economics (including hospitalization/readmission due to HF or other reason, ED visits, the duration of stay at each hospitalization/readmission), review of claims for prohibited medications and new diagnoses that may require discontinuation, and adverse events. In addition, information related to outpatient IV diuretics, inotropes and vasodilators and in-patient IV therapies as well will be considered relevant. Note that claims data that involves up to 36 months history to confirm eligibility into this study will not be part of the study database for analysis.

Participants will be of any gender, 18 years of age or older, and will have clinically stable, symptomatic HF with or without type 2 diabetes mellitus (T2DM) with a KCCQ overall summary score <80 prior to randomization, which represents New York Heart Association (NYHA) II and III participants.

Figure 1: Schematic Overview of the Study

1.3. Statistical Hypotheses for Trial Objectives

The primary effectiveness endpoint is the change in the KCCQ-TSS from baseline to Week 12. The null hypothesis to be tested here is that there is no difference between canagliflozin 100 mg and placebo in the treatment of symptomatic HF based on the primary effectiveness endpoint. For

the first key secondary effectiveness endpoint of change in daily step count from baseline to Week 12, the null hypothesis to be tested is that canagliflozin 100 mg is not different from placebo with respect to the mean change in daily step count.

The two hypotheses described above will be tested using a fixed-sequence (hierarchical) testing procedure to control the familywise type I error rate at 5% as follows:

1. (primary effectiveness endpoint): change from baseline to Week 12 in KCCQ-TSS for canagliflozin 100 mg versus the placebo
2. (first key secondary endpoint): change from baseline to Week 12 in daily step count for canagliflozin 10 mg versus placebo.

If the result of the 2-sided p-value from the first hypothesis (i.e., primary effectiveness endpoint) test is ≤ 0.05 , then the second hypothesis test result will be interpreted inferentially at the 5% significance level. This sequential testing approach will control the familywise type I error rate at 5%.

Hypotheses related to the second key secondary effectiveness endpoint (i.e., KCCQ individual domain scores defined by changes in physical limitation, quality of life, clinical summary, and overall summary from baseline to Week 12) as well as other exploratory endpoints will be tested at the nominal significance level (5%) without adjustment for multiplicity (or controlling type I error rate).

[figure not shown]
1.4. Sample Size Justification

The primary effectiveness endpoint is the change from baseline in the KCCQ-TSS at the end of the 12-week double-blind treatment period. Although a 5-point improvement in the KCCQ-TSS is generally viewed as clinically meaningful,^{2,12} recent studies^{7,8} have shown that improvements in the range of 3 to 5 points on the KCCQ-TSS are equally meaningful in the overall HF-related health status measured by the KCCQ over a 12-week time period. In considering the clinical significance of scores, it is important to separate mean changes for groups of participants, as compared with intra-individual changes. On the TSS, there are 7 items (4 for symptom frequency and 3 for severity/burden).^{3,11} Shifting a response on KCCQ questions 5 and 7 shifts the TSS score by 2.083 points on a 100-point scale. A shift in response for questions 3 and 9 shifts the score by 3.125 points and for items 4, 6, and 8, shifts the score by 4.166 points, assuming no missing responses. Thus, an intra-individual change of at least 2 categories (3 if the only change is in items 5 and 7) would exceed the 5-point threshold that has been shown to be clinically significant. When analyzing groups of participants, the mean difference across the entire population includes a distribution of participants with different magnitudes of individual change and a 3- to 5-point difference between groups reflects a significantly larger proportion of participants in one group, as compared with the other, who have clinically important improvements in their TSS.

Thus, based on the totality of evidence evaluating the clinical significance of the KCCQ,^{5,6,9,14} a between group difference of 3 points is considered clinically meaningful and the current study is powered to detect a mean change from baseline of 3 points in the KCCQ-TSS between canagliflozin 100 mg and placebo groups at Week 12. Assuming a significance level of 5% and a

standard deviation (SD) of 18 points for mean change in KCCQ-TSS, a total of 1,900 participants will be randomized in this study providing approximately 95% power. This sample size is adequate to account for a potential 5% to 10% dropout rate - that is, with a dropout as high as 10% [$n=1,710$], the statistical power remains $>90\%$.

After approximately 10 months, the planned enrollment in this study is not expected to reach the target of 1900 participants by the scheduled end of study enrollment window in the first quarter of 2021. Instead, the final anticipated enrollment may only be in the range of about 400-480 participants. Consequently, a reduction in total sample size of this magnitude will have impact on the statistical power for the assumed effect size as well as for various other plausible effect sizes, shown by the figures below. At 50% statistical power, an effect size of 3.5 points in the KCCQ change score (assuming standard deviation is 18) can be detected with a minimum sample size of 400. For power $\geq 80\%$, the required sample size has to be at least 445 if the expected mean difference in KCCQ-TSS change score over 12 weeks is as high as 4.8, assuming the pooled standard deviation is 18. An effect size of this magnitude for the KCCQ-TSS change score was reported in the recently concluded DEFINE-HF study¹⁷. Robust improvements over baseline were also reported for additional KCCQ domains in this study as well as in the SOLOIST study^{17,18}.

1.5. Randomization and Blinding

Central randomization will be implemented in this study. Participants will be randomly assigned to 1 of 2 study intervention groups based on a computer-generated randomization schedule prepared before the study by or under the supervision of the sponsor before initiation of the study.

Randomization will be balanced by using randomly permuted blocks and will be stratified by EF (HFREF or HFpEF) at study entry as recorded in the participant's electronic health record (EHR).

The interactive web response system (IxR) will generate a randomization code, participant randomization number, and kit number once consent is completed and the participant is confirmed eligible by the virtual principal investigator. The kit number will dictate the study intervention assignment and the matching study intervention bottle(s) to be shipped to the participant directly from the drug distribution vendor.

[figure not shown]
The IxR will provide the kit number of the study intervention bottle(s) to be dispensed for each randomly assigned participant of the double-blind treatment period. Based on these randomization codes, study intervention will be packaged and labeled in a manner that maintains the double-blinded nature of the study.

The drug depot will not be provided with randomization codes. The codes will be maintained within the IxR, which has the functionality to allow the virtual principal investigator or designee to break the blind for an individual participant.

Under normal circumstances, the blind should not be broken until participants have completed the 12-week, double-blind treatment period. The virtual principal investigator or designee may in an emergency determine the identity of the study intervention by contacting the IxR. In the event the blind is broken, the sponsor must be informed as soon as possible. The date and reason for the unblinding must be documented in the study database. All randomization codes will be released after completion of the study. Participants who have had their intervention assignment unblinded should continue to perform their scheduled evaluations.

1.6. Study Data Flow

Data flow in this study is facilitated by an automated integrated process that extracts clinical data from 3 sources: PRA mobile health platform [PRA mHP], Care Innovations, and Symphony. These data are loaded into PRA's Common Clinical Data Store (CCDS) where the data is accessible by JReview for data validation and analysis, as well as for extraction into RAW and SDTM datasets. This automated Extract-Transform-Load (ETL) process will utilize a data container on Amazon Web Services (AWS), referred to as the "Data Analytics Container" or "DAC", which is managed by PRA. A more detailed data flow diagram is provided in Appendix 5 of this SAP.

The PRA mHP platform serves as the main hub for source data capture on the CHIEF-HF study. It captures eConsent, information entered by Health Network Systems (HNS) from a participant's electronic medical records (EMRs), participant status overseen by Care Innovations (CI), randomization through integration with Endpoint IRT, drug shipment through integration with Marken, primary and secondary endpoint data from ePROs (KCCQ, PGI-S, PGIC), dosing compliance, as well as activity measured by the Fitbit watch. PRA mHP data will go into the DAC via a direct database connection. Medical and pharmacy claims data is contained within Symphony

Health Solutions and exists as completely de-identified data. This includes data used in the study to review and analyze adverse events, healthcare resource utilization (HRU) and health economics (including hospitalization/readmission due to Heart Failure [HF] or other reason, Emergency Department (ED) visits, the duration of stay at each hospitalization/readmission), as well as review of prohibited medications and new diagnoses that may require discontinuation.

Symphony claims data will be pulled into the DAC for participants randomized into the study via PRA mHP eConsent and will be mapped to SDTM as detailed in the SDTM specifications relevant to the study protocol and SAP. The collection timeframe for claims associated with AEs of special interest will begin on the Informed Consent Date through the End of Treatment + 30 days. The collection timeframe for Pharmacy claims of prohibited concomitant medications (SGLT2i) will begin on the ICF date through End of Treatment. The collection timeframe for claims associated with Health Resource Utilization will begin on the ICF Date through the 9-month observation period.

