- d. Includes up to 36 months of historical medical and pharmacy claims data for eligibility confirmation. This data collection will begin upon signing of the informed consent.
- e. Participant-reported adverse events to the call center occurs from the time of informed consent until 30 days after the end of treatment (ie, the last dose of study intervention). Adverse events from medical claims data occurs from the time of informed consent to the end of study.

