6.1. Adverse Events

All AE data summaries will be based on the safety analysis set except where stated otherwise. A treatment emergent AE is defined as an event that occurs after the first dose of study intervention (Study Day 1) and/or worsens in severity during the double-blind treatment period.

Adverse events self-reported to the Call Center will be assessed by Janssen Global Medical Safety (GMS) for start and end dates, causality and meeting SUSAR reporting requirements. If the specific dates pertaining to the self-reported AEs are unknown, there will be limited follow-up for resolution. For any events still ongoing at the end of the study, there will be no follow up (as the Call Center will be closed at that point) possible. Adverse events will be coded according to MedDRA and will be reported by preferred term for each randomized intervention group. Janssen Data Management will request a listing of all AEs/SAEs reported to the Call Center from the Janssen GMS. This listing will be shared with PRA (external vendor) to convert the information

into the SDTM format and for inclusion in the final SDTM data package for summary by various subgroups (e.g., T2DM and non-T2DM).

Adverse events collected through the claims database will be analyzed separately for the 12-week treatment period + 30 days after last dose and the 9-month entire study period respectively. It is assumed that claims database will have dates of service provided (procedure dates, office visits, hospital admissions, etc.) but not actual start/end dates of events prior to claims being filed. Therefore, no imputation of AE start/end dates will be feasible based on the claims data. Dates of service(s) rendered to participants during the study (i.e., starting from the time informed consent is signed until the end of double-blind treatment plus 30 days) will be taken into account. The claims data will utilize ICD codes to identify the SAEs and AEs of interest which are defined in the protocol and for the final analysis. The AEs of interest include all severe hypoglycemic events, acute kidney injury, fractures, diabetic ketoacidosis, and lower limb amputation. In addition, hypotension, Fournier's gangrene, genital mycotic infections, urinary tract infections (including urosepsis and pyelonephritis), increased urination and hypersensitivity reactions (including angioedema and anaphylaxis) will be considered for coding and final analysis.

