For the prohibited medications, analysis period will include data from the date of informed consent until the end of double-blind treatment period. For all other concomitant medications, analysis period will include data from the date of informed consent until the end of the study. For the HRU data analysis, information collected from date of informed consent until the end of study will be considered in the final analysis.

For both the double-blind treatment period + 30 days after last dose and the 9-month entire study period, descriptive summaries (numbers and percentages) of participants having an SAE/AE of interest will be produced, including by participant's diabetes status (T2DM and non-T2DM) and by randomized intervention group. Discontinuations (and reported reasons) will be summarized by randomized intervention group based on available claims data.

There will be no reconciliation/analysis of SAE/AE data that are self-reported to the Call Center with the data obtained from the claims database.

A listing will be presented for treatment emergent hospitalizations and deaths for each randomized intervention group. AEs occurring between informed consent and the day prior to the first dose of study intervention will also be listed. This listing will be based on participants with informed consent into the study. Depending on the claims/pharmacy data, AEs occurring in participants who used prohibited (commercially available SGLT2is other than the study intervention, canagliflozin) will also be listed.

Based on pharmacy profiles of the participants after-consent in this study, the total number of participants concomitantly receiving UGT inducers during the double-blind treatment period will be summarized combined across both study intervention groups. If the number of such participants is >2% of the total 1,900 targeted for enrollment in this study, the users and non-users of UGT inducers will be summarized by each study intervention group as well and examined further (as

necessary) for any relationship to key study outcomes (eg, PRO endpoints and clinical outcomes reported in claims).

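### The SAP stops claims for adverse events of interest at end of treatment plus 30 days in two places, yet promises a 9-month by-arm summary of them

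*SAP*

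**What the plan says.** SAP 1.6 (Study Data Flow) gives each category of claims its own window. For safety events, the window for claims on AEs of special interest "will begin on the Informed Consent Date through the End of Treatment + 30 days". For resource utilization (HRU), in the same paragraph: "The collection timeframe for claims associated with Health Resource Utilization will begin on the ICF Date through the 9-month observation period". It gives no window for claims that identify serious AEs.

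SAP 6.1 (Adverse Events) says that AEs from the claims database "will be analyzed separately for the 12-week treatment period + 30 days after last dose and the 9-month entire study period respectively". The same paragraph then says that the service dates taken into account run from consent to the end of double-blind treatment plus 30 days. Later in 6.1, "For both the double-blind treatment period + 30 days after last dose and the 9-month entire study period", the SAP promises counts and percentages "of participants having an SAE/AE of interest will be produced, including by participant's diabetes status (T2DM and non-T2DM) and by randomized intervention group".

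Protocol 1.3, footnote e, sets the longer collection window: "Adverse events from medical claims data occurs from the time of informed consent to the end of study". Protocol 8.3.1 repeats it. For analysis, 8.3.1 names two by-treatment aggregations of claims data: AEs for the treatment period plus 30 days, and serious AEs for the 9-month study.

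**The concern.** The SAP specifies a 9-month table, but its extraction rule, and one of its own analysis sentences, stop the input for part of that table well before Month 9. A programmer who follows SAP 1.6 or the service-date sentence in 6.1 would have no dedicated input for AEs of interest after about Day 114. A programmer who follows the two-period sentences in 6.1 would expect input to Day 252.

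At stake is how the table is read. After treatment plus 30 days the call center no longer captures events, so claims are the only source. In a table labelled as 9 months, events that were never extracted look the same as events that did not occur. The SAP gives no reason for a pull narrower than the protocol's collection window.

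**Working it through.** Neither document gives a figure on this point, so there is nothing to reproduce. The check is a comparison of windows plus day counts.

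**Inputs**
- End of treatment: Day 84 ± 3 (Protocol 1.3; SAP Appendix 3).
- End of study: Day 252 ± 7 (same sources).
- Cut-off for AEs of interest: end of treatment + 30 days (SAP 1.6; service-date sentence in SAP 6.1).

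**Windows side by side**

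| Source | Claims events covered | Ends at |
|---|---|---|
| SAP 1.6 | AEs of special interest | Treatment + 30 days |
| SAP 6.1, service dates | Claims AEs | Treatment + 30 days |
| SAP 6.1, analysis periods and summaries | SAEs and AEs of interest | Both treatment + 30 days and 9 months |
| SAP 1.6 | HRU | 9 months |
| Protocol 1.3 and 8.3.1, collection | Claims AEs | End of study |
| Protocol 8.3.1, by-treatment aggregation | AEs / serious AEs | Treatment + 30 days / 9 months |

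SAP 1.6 speaks of events of special interest and SAP 6.1 of events of interest. Neither document gives a separate special-interest list, and Protocol 8.3.4, SAP 5.1.2 and SAP 6.1 name one common set, so I treat them as the same events.

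**Day counts, from Day 1**
- Cut-off = 84 + 30 = Day 114.
- Uncovered = 252 − 114 = 138 days; 138/252 = 54.8%.
- Post-treatment time covered = 30/(252 − 84) = 30/168 = 17.9%.

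**Across the visit windows**
- Smallest gap: 87 + 30 = 117; 245 − 117 = 128 days; 128/245 = 52.2%.
- Largest gap: 81 + 30 = 111; 259 − 111 = 148 days; 148/259 = 57.1%.

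**If end of treatment means each participant's own last dose.** This is an assumption about SAP 1.6, although SAP 6.1 does count its 30 days from last dose. Early stoppers then lose more:
- Last dose Day 42: cut-off Day 72; 180/252 = 71.4% uncovered.
- Last dose Day 28: cut-off Day 58; 194/252 = 77.0% uncovered.
- Last dose Day 14: cut-off Day 44; 208/252 = 82.5% uncovered.

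Under that reading the loss would differ by arm if discontinuation did.

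**The case against.** **General statements point to Month 9.** SAP 1.2 and the opening of SAP 2 say that claims collection continues through Month 9, and the protocol agrees. This stands as far as it goes: truncation follows only if the specific windows override the general ones. But the short window appears in both the extraction text and the analysis text, so it is not a stray phrase, and a programmer would normally follow the specific rule.

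**The HRU pull may fill the gap.** It runs through 9 months from the same claims source. Even on the narrow list in Protocol 8.2.4 it takes in hospitalizations and emergency visits. SAP 5.4.2 describes HRU more broadly, in terms that could include outpatient care. This largely stands for events that led to hospitalization or an emergency visit. It does not settle the matter, because nothing says that HRU claims feed the AE table, and Protocol 9.4.3 lists AEs of interest alongside SAEs leading to hospitalization or emergency visits, as a separate item.

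**The excess may lie in SAP 6.1.** The 1.6 window matches the period for which the protocol aggregates claims AEs by arm; only serious AEs are aggregated over 9 months. This stands, and it is why limiting the table is as legitimate a remedy as extending the pull.

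**The stakes are limited.** The treatment-plus-30-days summary is fully covered. The later period is off drug, after participants have been told their allocation, and outside the SAP's treatment-emergent definition. This also stands.

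A reader might infer that late amputations, fractures and kidney injury are bound to be undercounted. The documents do not support that. Such events, when they lead to hospitalization or an emergency visit, are within the 9-month HRU pull, and the documents leave open whether that pull is used for the AE table.

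**Conclusion.** The inconsistency is real and is in current text: between SAP 1.6 and SAP 6.1, within 6.1 itself, and between the SAP windows and the protocol's collection period. If the specific windows govern, about 138 of 252 days (55%; 52% to 57% across the visit windows) of the 9-month table has no dedicated extraction for AEs of interest.

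How many events that would cost cannot be estimated from the documents. The loss would fall mainly on events handled only in outpatient care. That rests on two assumptions: that the specific windows override the general statements, and that HRU claims either do not feed the AE table or do not carry those outpatient events. The affected output is a descriptive off-treatment safety table. No primary, secondary or other tested endpoint depends on it, but it should be corrected because its label and its input disagree.

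**What to change.** Choose one of two routes:

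- **(a) Extend.** Run the claims window for AEs of interest to end of study in both SAP 1.6 and the service-date sentence of SAP 6.1. Changing 1.6 alone is not enough, because the service-date sentence would still cut the table at the same point.
- **(b) Limit.** Restrict the 9-month analysis and summary in SAP 6.1 to serious AEs, matching the by-treatment aggregation in Protocol 8.3.1, and show AEs of interest for treatment plus 30 days only. The pull for AEs of interest would then still be shorter than the protocol's collection window, so the SAP should say that this is intended.

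In either case, state in SAP 1.6 that SAE claims are pulled through Month 9, and make the service-date sentence in 6.1 agree. It would also help to say whether HRU claims may feed the AE tables.

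The cost is an edit to the SAP and the extraction specification. The same claims source is already pulled through 9 months for HRU, so no new data source or participant contact is needed.
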